**Table 2 List of Laboratory Tests**

---

Hematology:	Serum Chemistry:
Hematocrit	Albumin
Hemoglobin	Alkaline phosphatase
Mean corpuscular hemoglobin	Alanine aminotransferase (ALT)
Mean corpuscular hemoglobin concentration	Amylase
Mean corpuscular volume	Aspartate aminotransferase (AST)
Platelet count	Blood urea nitrogen
Pancreatic enzymes	Calcium
Red blood cell count	Calculated creatinine clearance
White blood cell count with differential	Carbon dioxide
	Chloride
	Creatinine
	Creatine kinase and subtypes
Urinalysis:	Gamma-glutamyl transferase
Appearance	Globulin
Bilirubin	Glucose (non-fasting)
Color	High-density lipoprotein (HDL)
Glucose	Immunoreactive trypsinogen
Ketones	Lactate dehydrogenase
Leucocyte esterase	Lipase
Microscopic examination of sediment a	Low-density lipoprotein (LDL)
Nitrite	Magnesium
Occult blood	Phosphorus
pH	Potassium
Protein	Sodium
Specific gravity	Total bilirubin
Urobilinogen	Direct bilirubin
	Total cholesterol
Hormone Panel:	Total protein
Adrenocorticotropic hormone (ACTH) Follicle Stimulating Hormone	Triglycerides
Testosterone (total and free)	Uric acid
Pregnancy:	Urine Drug Screen (UDS):
Urine Pregnancy (only for females not postmenopausal or surgically sterile for at least 1 year)	Opioids b
Serum Pregnancy	Cocaine
	Amphetamines
	Methadone
Screening:	Cannabinoids
Hemoglobin A1c	Barbiturates
HIV-1 and -2 antibodies	Benzodiazepines
PTT	Methamphetamine
PT with INR	Phencyclidine
Serum pregnancy	

---

Anti-HIV = human immunodeficiency virus antibodies; hCG = human chorionic gonadotropin; INR = international normalized ratio; IRT = immunoreactive trypsinogen; PT = prothrombin time; and PTT = partial thromboplastin time.

a Microscopic examination of sediment will be performed only if the results of the urinalysis evaluation are positive (microscopic examination may include but is not limited to WBC count, RBC count, casts, and crystals).

b Oxycodone may not show up in all opiate assays and should be assessed separately.

### 6.6.2 Sample Collection, Storage, and Shipping

All blood sampling will be by individual venipuncture or with the use of a saline lock. Blood and urine sample collection and processing procedures will be outlined in a separate reference manual to be provided to the site.

### 6.6.3 Reference Ranges

Up-to-date reference ranges for the above investigations must be obtained for the laboratory performing analyses prior to the start of the study and be updated as appropriate during the course of the study.

### 6.6.4 Laboratory Results Review

The Investigator will review the results and comment on the laboratory results sheet for all abnormal values, identifying those that are abnormal but not clinically significant as well as those that are significantly abnormal. The Investigator will sign and date the laboratory results sheet to indicate that the review has taken place.

**Clinical Laboratory Changes:** It is the Investigator's responsibility to review the results of all laboratory tests as they become available. This review will be documented by the Investigator on the laboratory report. For each abnormal laboratory test result, the Investigator needs to ascertain if this is a clinically significant abnormal change from baseline for that individual subject.

## 6.7 Pharmacokinetic Assessments

Blood samples for population PK analysis will be collected from roll-over subjects only at the time points indicated in the PK sampling schedule ([Appendix 6](#)). Once at least 75 roll-over subjects have completed Injection 6 (Week 25, Day 169) the sites will be notified that no more PK samples will be required to be collected from the roll-over subjects for the duration of the study. The plasma concentrations of buprenorphine and norbuprenorphine will be quantified using specific and validated liquid chromatography tandem mass spectrometry methods. A laboratory manual for PK sample collection, processing, storage, and shipping will be supplied.

However, for all subjects (*de novo* and roll-over) throughout the study, a PK sample will be taken as soon as possible after any SAE is reported. If possible, an additional sample should be collected when the SAE has been resolved.

The exact times (to the minute) of PK blood sampling as well as the exact times of drug administration will be recorded in the source and eCRF.

## 6.8 Administration of Study Drug

The study drug will be assigned by an IWRS system. Injections will be administered by a physician or suitably-qualified designee (e.g., physician, nurse, nurse practitioner, PA) who has been delegated to perform the task. Study drug will be supplied only to subjects participating in

the study. The Investigator agrees not to allow the study drug to be administered from, nor stored at, any site other than the study site agreed upon with the Sponsor.

See [Appendix 7](#) for detailed descriptions of dosing for the SUBOXONE sublingual film. Detailed instructions for the preparation and administration of RBP-6000 are in [Appendix 8](#).

If at an injection visit there is a safety concern with administration of RBP-6000, after discussion with the medical monitor or sponsor, dosing can be delayed up to one week. In the event this occurs, the subsequent doses will be delayed. There must be at least 26 days between injections of study medication.

All used syringe components will be disposed of into an appropriate secure biohazard container or per the SOPs at the study site.

All used IMP packaging (e.g., carton, foil pouch) will be retained at the study site until the CRA conducts a visit to perform reconciliation. After the reconciliation is completed, the used IMP packaging may then be disposed of per the SOPs at the study site.

Unused IMP and returned SUBOXONE sublingual film must be available for verification by the Sponsor's site monitor during on-site monitoring visits. The return of unused or used returned IMP for destruction will be documented on the drug return form.

## 6.9 Safety and Suicidality Assessments

Safety will be assessed by AEs, vital signs, ECGs, clinical laboratory assessments, local injection site grading scale, injection site pain VAS, and eC-SSRS responses. See the SOE for specific timing of assessments ([Appendix 1](#), [Appendix 2](#), [Appendix 3](#), [Appendix 4](#), and [Appendix 5](#)).

### 6.9.1 Local Injection Site Tolerability

#### 6.9.1.1 Injection Site Grading

Local injection site grading will be performed by the Investigator or a trained and qualified health care professional, according to the SOE in [Appendix 2](#), [Appendix 3](#), [Appendix 4](#), and [Appendix 5](#). Injection sites will be assessed for pain, tenderness, erythema/redness, induration, or swelling. Local injection site tolerability will be assigned a severity grade, including none (grade 0), mild (grade 1), moderate (grade 2), severe (grade 3), or potentially life threatening (grade 4) utilizing the Injection Site Grading Scale in [Appendix 15](#). The local injection site grading assessment will be completed electronically on injection days immediately after each injection (within 10 minutes) and at 1 hour ( $\pm$  15 minutes). For Injection 1 only, local injection site grading will be completed 24 hours ( $\pm$ 4 hours) after the injection.

#### 6.9.1.2 Injection Site Pain Visual Analogue Scale (VAS)

Injection site pain will be assessed by the subject at each injection visit electronically with a 100mm VAS scale, where 0 represents no pain and 10 represents maximum pain ([Appendix 16](#)). The injection site-pain VAS scores will be obtained (after the completion of the injection) within

1 minute and then at 5, 10, 15, 30, and 60 minutes ( $\pm 5$  minutes). The timing of the Injection Site Pain VAS should be measured from the end of the injection. In addition to rating pain levels by marking on the line the point they feel best represents their perception of their current state, the subject will also answer the following question with either a Yes or No: Are you currently experiencing any burning or stinging at the injection site?

## 6.9.2 Suicidality

### 6.9.2.1 Columbia Suicide Severity Rating Scale

The eC-SSRS will be administered according to the SOE in [Appendix 1](#), [Appendix 2](#), [Appendix 3](#), [Appendix 4](#), and [Appendix 5](#). The eC-SSRS is a questionnaire designed for assessment of suicidal ideation and behavior in adolescents and adults (Posner 2011). The questionnaire will be administered as an electronic, self-rated version (eC-SSRS). Clinical trial versions of the questionnaire are available for trial screening and follow-up visits. A sample section from the Baseline/Screening eC-SSRS and the follow-up eC-SSRS are presented in [Appendix 10](#) and [Appendix 11](#), respectively.

If a subject becomes suicidal during the study, the investigator should provide the appropriate treatment to the subject. If the suicidality is deemed to be related to IMP and it is within 14 days of an injection, the depot may be removed ([Section 6.14.1](#)).

The eC-SSRS should be completed prior to SUBOXONE and RBP-6000 injection and at approximately the same time each day  $\pm 2$  hours.

If, there is a positive on the eC-SSRS after screening the subject will be evaluated by the investigator for continuation in the study. If needed, the investigator can consult with the medical monitor on continuation in the study of subjects with a positive eC-SSRS.

## 6.10 Adverse Events Assessments

### 6.10.1 Definition

In accordance with ICH and US FDA guidance, any untoward medical occurrence incurred by a subject that occurs after the first study-related procedure to the completion of the last EOS/ET visit or start of treatment on the INDV-6000-301 study and is associated with the use of the drug, regardless of the presence of causal relationship, is a reportable AE. AEs that are ongoing at the time a subject rolls-over from the RB-US-13-0001 study will be recorded in the eCRF.

Abnormal results of diagnostic procedures, including laboratory test abnormalities, are considered AEs if they:

- Result in discontinuation from the study,
- Require treatment or any other therapeutic intervention,
- Require further diagnostic evaluation (excluding a repetition of the same procedure to confirm the abnormality), or

- Are associated with clinical signs or symptoms that would have a significant clinical impact, as determined by the Investigator.

### 6.10.2 Performing Adverse Events Assessments

The Investigator is ultimately responsible for assessing and reporting all AEs as outlined in the protocol. The assessment of AEs may be delegated to a medically qualified sub-investigator, trained on this study protocol, who is listed on the FDA Form 1572 or equivalent document, and on the delegation of authority form.

AEs should be volunteered by the subject or solicited from the subject using a standard statement, obtained from examination of the subject at a clinic visit, or from observations of clinically significant laboratory values or special examination abnormal values. If an event assessed by one of the study scales requires intervention, or if in the opinion of the Investigator, it is clinically significant, then it will be reported as an AE.

All AEs are to be assessed and recorded in a timely manner and followed to resolution or until the Investigator determines that there is not an anticipated resolution. Each AE is to be documented with reference to severity, date of occurrence, duration, treatment, and outcome. Furthermore, each AE is to be classified as being serious or non-serious. In addition, the Investigator must assess whether the AE is drug-related or not. Changes in severity of AEs should be documented as one event at the maximum severity that occurred during the study.

### 6.10.3 Timing

AEs will be captured from the time the subject gives informed consent until the subject completes the study.

Surgical procedures, planned before enrollment of the subject in the study, are not considered AEs if the condition was known before study inclusion. In this case the medical condition should be reported in the subject's medical history.

If a subject experiences the onset of an SAE within 30 days following study completion and in the opinion of the Investigator, that SAE is associated with the study, it will be followed and reported as described in Section [6.10.9.2](#).

If a SAE occurs a PK sample will be taken as soon as possible after the event is reported. If possible, an additional sample should be collected when the SAE has been resolved.

### 6.10.4 Severity

Adverse events with changes in severity should be documented as one event at the maximum severity.

Intensity	Definition
Mild	Causes transient or mild discomfort ; no limitation of usual activities; no medical intervention required
Moderate	Causes mild to moderate limitation in activity; some limitation of usual activities: no or minimal medical intervention or therapy is required.
Severe	Causes marked limitation in activity; some assistance is usually required; medical intervention or therapy is required; hospitalization is probable.

The term “severe” is used to describe the intensity (severity) of a specific event (as in mild, moderate, or severe); the event itself, however, may be of relatively minor medical significance (such as a severe headache). This is not the same as “serious,” which is based on subject/event outcome or action criteria usually associated with events that pose a threat to a subject’s life or functioning. Seriousness (not severity) serves as a guide for defining regulatory reporting obligations.

#### 6.10.5 Relationship

The Investigator or a medically qualified sub-investigator, trained on this study protocol, listed on the 1572 form or equivalent document and on the delegation of authority form is responsible for determining the AE relationship to the investigational product.

The following categories will be used to define the relationship of an AE to the administration of the investigational product:

- Not Related: Data are available to identify a clear alternative cause for the AE other than the investigational product.
- Related: The cause of the AE is related to the investigational product and cannot be reasonably explained by other factors (e.g., the subject’s clinical state, concomitant therapy, and/or other interventions).

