Test Product, Dose, and Mode of Administration: 300 mg buprenorphine in RBP-6000, subcutaneous injection 100 mg buprenorphine in RBP-6000, subcutaneous injection
Duration of Study Treatment: This will be a multiple-dose study, with the first investigational product administration (RBP-6000 containing 300 mg buprenorphine) on Day 1. The expected maximum duration of participation for de novo subjects is up to approximately 55 weeks, consisting of up to 7 days of screening, up to 14 days SUBOXONE sublingual film Run-In, up to a 48-week open-label treatment period, and a 4-week safety follow-up telephone call. The expected maximum duration of participation for roll-over subjects is up to approximately 31 weeks, consisting of up to a 7-day screening period, up to 14 days SUBOXONE sublingual film Run-In, a 24-week open-label treatment period, and a 4-week safety follow-up telephone call. Subjects who enroll in the INDV-6000-301 study are not required to complete the safety follow-up telephone call.
Safety Assessments: Safety objectives for this study are to evaluate the safety and tolerability of RBP-6000 (100 mg and 300 mg) SC injection treatment in subjects with opioid use disorder. Safety assessments will include the following: frequency of all AEs, serious AEs (SAEs), discontinuations from study due to AEs; local injection site tolerability (e.g., injection site grading); injection site pain using a subject-reported VAS; suicidality using the eC-SSRS, use of concomitant medications; changes in clinical laboratory results; vital sign measurements; 12-lead ECGs, which will be interpreted by a central facility; physical examination results; body weight, height, and body mass index (BMI), and abdominal fat measurement (waist-to-hip ratio).
Clinical Outcome Assessments: Clinical outcome assessments will include the UDS for opioids and other drugs; self-reported use of illicit opioids, other drugs, and alcohol on the TLFB; COWS, SOWS, and Opioid Craving VAS.

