TEAEs are those that started following the first dose of RBP-6000 in this study or were present prior to the first dose of RBP-6000 in this study regardless of causality and increased in severity following administration of RBP-6000 regardless of causality ≤30 days after the last dose of RBP-6000. All AEs which change in severity or relationship to RBP-6000 are assigned a new start date and captured as a new AE. AEs include those events that are ongoing at the time a subject rolls-over from the RB-US-13-0001 but these events will not be considered treatment-emergent.

Sponsor: Indivior Inc.
Protocol no: RB-US-13-0003

Run-In Adverse Events

An AE for the run-in period is an AE that either commenced during the run-in period or was present prior to the initiation of run-in, but increased in severity during run-in, regardless of causality, and prior to the first injection of RBP-6000.

Outcome of Death

Any AE with an outcome of fatal or study discontinuation due to death.

Subjective Opioid Withdrawal Scale Total Score

The SOWS total score is defined as the sum of the responses to the 16 questions as indicated by the subjects on how they feel at the time of completed the questionnaire including anxiousness, yawning, perspiring, teary eyed, runny nose, goosebumps, shaky, hot flushes, cold flushes, bones and muscle achiness, restlessness, nausea, vomiting, muscle twitching, stomach cramps, and feeling like using now. Each answer to a corresponding question is assigned a value between 0 and 4. If 3 or more responses are missing, then a total score will be set to missing. If less than 3 responses are missing, then the total score will be normalized.

Suicidal Ideation Scoring

The suicidal ideation score ranges from 0 to 5 and depends on the answers to the suicidal ideation portion of the eC-SSRS. The score is the maximum suicidal ideation category (in the following order: 1 = wish to be dead, 2 = Non-specific active suicidal thoughts, 3 = active suicidal ideation with any methods (not plan) without intent to act, 4 = active suicidal ideation with some intent to act, without specific plan, and 5 = active suicidal ideation with specific plan and intent) present at the assessment. If all answers to these questions are "No" then the suicidal ideation score is 0.

Suicidal Ideation Intensity Rating:

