9.6 Primary Safety Analyses

9.6.1 Incidence of Adverse Events

9.6.1.1 Adverse Events

Imputation of AE (for determination of TEAE only) and concomitant medication start and stop dates:

Start Date: If only 'day' is missing, and the month and year are not the same as the month of first dose, then impute day with '01'. Otherwise, if the month and year are the same as the first dose date, use the first dose date. If 'day' and 'month' are missing, and 'year' is not missing, then impute month and day with month and day of the first dose date (assuming same 'year'). If 'day' and 'month' are missing and 'year' is not missing and is not the same year as first dose date, then impute with '01' for both 'day' and 'month'. If the start date is completely missing, it will be set to the first dose date.

Stop Date: If only 'day' is missing, impute day with last day of the month. If 'day' and 'month' are missing, and 'year' is not missing, then impute month with '12' and day with '31' (or date of study discontinuation/completion if earlier than 12-31 and year is the same as the year of discontinuation). If the stop date is completely missing, it will be set to the date of study discontinuation/completion. A stop date will not be applied to ongoing AEs or ongoing medications.

Treatment-related Adverse Events

Any AE with a relationship to study treatment of 'Related' or missing will be considered a treatment-related AE as determined by the Investigator.

A summary of treatment-emergent AEs will be presented for the Safety Analysis Set and the Run-In Safety Analysis Set, including the number of events reported, the number and percentage of subjects reporting at least one AE, the number and percentage of subjects with the following:

- Related AEs
- SAEs
- Related SAEs
- AEs with an outcome of death
- Severe TEAEs
- AEs leading to discontinuation

A breakdown of the number and percentage of subjects reporting each AE categorized by SOC and PT coded according to the MedDRA dictionary version 17.1 will be presented for the Run-In period using the Run-In Safety Analysis Set and for the open label RBP-6000 treatment period using the Safety Analysis Set. Note that counting will be by subject not event and subjects are only counted once within each SOC or PT. AEs/TEAEs related to SUBOXONE/study treatment will be presented in a similar manner.

A further tabulation of events experienced by $\geq 5\%$ of subjects by SOC and PT will be presented for the Safety Analysis Set.

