9.6.1.2 Serious Adverse Events

SAEs and treatment-related SAEs will be summarized separately by SOC and PT for the Run-In Safety Analysis Set and the Safety Analysis Set.

All SAEs recorded on the CRF will be listed for all screened subjects.

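### Causality is defined only against RBP-6000, yet the SAP reports run-in adverse events as SUBOXONE-related, so those related rows have no fixed meaning

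*Protocol*

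**What the plan says.** Protocol 6.10.5 sets out two categories, Related and Not Related, under the sentence "The following categories will be used to define the relationship of an AE to the administration of the investigational product". An AE is Not Related when the data point to a clear cause other than that product. It is Related when other factors cannot reasonably explain it.

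The protocol uses the term for RBP-6000. The synopsis, under duration of treatment, describes a multiple-dose study "with the first investigational product administration (RBP-6000 containing 300 mg buprenorphine) on Day 1". Section 5.1.2 lists only RBP-6000 as investigational product, with SUBOXONE film described apart in 5.1.1. Section 6.8 keeps the two separate: "Unused IMP and returned SUBOXONE sublingual film must be available for verification". SAP 5.0 does the same: "All AEs which change in severity or relationship to RBP-6000 are assigned a new start date".

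The SAP adds a Run-In Safety Analysis Set (1.1, 6.2) and defines a run-in AE as one that began or worsened in the run-in, before the first injection. Its overview in 9.6.1.1 includes related AEs and related SAEs for that set. For the tables by SOC and PT it says: "AEs/TEAEs related to SUBOXONE/study treatment will be presented in a similar manner". Section 9.6.1.2 adds: "SAEs and treatment-related SAEs will be summarized separately by SOC and PT for the Run-In Safety Analysis Set and the Safety Analysis Set". Section 9.6.1.3 does likewise for treatment-related discontinuations. An AE whose relationship is recorded as Related "or missing will be considered a treatment-related AE as determined by the Investigator".

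**The concern.** The run-in tables ask whether the film caused the event. The only causality scale in the protocol asks whether RBP-6000 did. In the run-in, SUBOXONE is itself a cause other than the investigational product, so the definition sends film-caused events to the wrong category. The list of changes from protocol in SAP 1.1 records the new analysis set but no matching change to causality.

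At stake is the meaning of the run-in rows for related AEs, related SAEs and related discontinuations. An event could be left out because the definition was followed, or counted because nothing was entered. The rows could also mean different things for de novo and roll-over subjects, which is the split by which the SAP presents its summaries.

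**Working it through.** The documents give no run-in AE incidence, relatedness rate or missing rate, so there is no stated figure to reproduce. The check has two steps.

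**Step 1: follow one run-in AE through the text.**

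- De novo subject, AE caused by the film, Protocol 6.10.5 followed: there is a clear cause other than RBP-6000, so the code is Not Related. The SAP's SUBOXONE-related table leaves the event out.
- Same AE, relationship missing: SAP 9.6.1.1 counts it as related, so the event is in the table.
- Roll-over subject given RBP-6000 in RB-US-13-0001: Related may refer to that earlier drug, and the table would show it as SUBOXONE-related.

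The third case is pharmacologically possible. Protocol 1.4.2 gives terminal half-lives of 1078 h (50 mg) to 1573 h (200 mg) after single doses. I assume 28 days from the last earlier injection to Day 169, then up to 7 days to the start of film and 14 days of run-in: 28 + 7 + 14 = 49 days. With simple exponential decay, the fraction remaining is 0.5^(24 × days / half-life in hours):

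- 28 days, 1573 h: 0.5^(672/1573) = 0.74
- 49 days, 1078 h: 0.5^(1176/1078) = 0.47

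So roughly 47% to 74% would remain. This is a rough guide, because the half-lives come from single doses and decay may not be simple. Roll-over subjects who had placebo carry nothing over.

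**Step 2: bound the related row.** The tables count subjects, not events (SAP 9.6.1.1), over everyone with at least one SUBOXONE dose in the run-in (SAP 6.2). Let q be the share of run-in subjects with any AE, r the share of AEs coded Related and m the share with missing causality. With one AE per subject:

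related row = q × (r + m)

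Since r + m lies between 0 and 1, the row lies between 0 and q. The values of q below are assumptions, and 600 is planned enrolment used as an assumed denominator; the size of the run-in set is not stated.

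| Assumed q | Range of related row | Subjects of 600 |
|---|---|---|
| 10% | 0 to 10% | 0 to 60 |
| 20% | 0 to 20% | 0 to 120 |
| 30% | 0 to 30% | 0 to 180 |
| 50% | 0 to 50% | 0 to 300 |
| 1% (SAEs) | 0 to 1% | 0 to 6 |

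The missing rule can fill the row alone. With no AE coded Related, k AEs per subject and independent missingness, row = q × [1 − (1 − m)^k]. At q = 20%:

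- k = 1: 1.0% for m = 5%, and 4.0% for m = 20%
- k = 3: 20% × (1 − 0.95³) = 2.9%, and 20% × (1 − 0.80³) = 9.8%

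With a proper SUBOXONE item the uncertainty shrinks to q × m. Take q = 20%, m = 5% and half of the completed entries Related (all assumed). The row is 20% × 0.5 × 0.95 = 9.5% with missing excluded, and 9.5% + 20% × 5% = 10.5% with missing counted as related.

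**The case against.** The best counter-argument is that the SAP was written against a CRF dated 22SEP2016, which is not among the documents. The sentence "AEs/TEAEs related to SUBOXONE/study treatment will be presented in a similar manner" can be read as two pairs: run-in AEs to SUBOXONE, and TEAEs to study treatment. That would fit a CRF with its own SUBOXONE item. The protocol's wording is also not uniform. Section 6.10.2 says "In addition, the Investigator must assess whether the AE is drug-related or not" without naming the drug, section 5.2.1.2 once calls the induction film study drug, and section 5 treats both products as study treatments. This stands as a limit: miscoding is a risk, not a demonstrated fact. It does not close the gap, because neither document mentions a SUBOXONE item and 6.10.5 gives investigators no definition for one.

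Four stronger readings are tempting and not supported.

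- A reader might infer that the run-in tables could read anywhere from 0% to 100%. They count subjects over the whole run-in set, so the ceiling is the any-AE (or any-SAE) incidence. Only the share of run-in AEs called related could span 0% to 100%, and only if all sites behaved alike.
- A reader might infer that sites will leave the field blank. Section 6.10.2 makes the assessment mandatory, section 10.7 requires an explanation for missing data, and section 10.11 provides edit checks and queries.
- A reader might infer that every run-in AE must be Not Related because RBP-6000 has not yet been given. Section 6.10.5 contains no such rule; it requires a clear alternative cause.
- A reader might infer that the SAP labels run-in SAEs as SUBOXONE-related. SUBOXONE is named only for AEs; the SAE and discontinuation tables say treatment-related.

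It is also fair that the impact is limited. The primary objective is RBP-6000 safety, and Protocol 9.5.1.1 confines the safety analysis to events after RBP-6000.

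**Conclusion.** The mismatch is in the text and should be corrected. Protocol 6.10.5 defines causality against RBP-6000 only, while the SAP reports relatedness for events that began or worsened before the first injection in this study, for AEs expressly to SUBOXONE. Followed as written, the definition puts film-caused events in the wrong category, so this is more than a missing detail.

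Each related row can lie between 0 and the incidence of any run-in AE, SAE or discontinuation AE, as the case may be. Those incidences are not stated; the ranges above rest on assumed values. Until the product is named, the related share of run-in AEs cannot be interpreted or compared between de novo and roll-over subjects.

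The conclusion assumes that sites apply 6.10.5 as written and that no separate SUBOXONE item exists. If the CRF has one, the remedy reduces to saying so and defining it. The all-causality run-in tables and the AE and SAE listings are unaffected, and nothing here undermines the primary analysis of TEAEs on RBP-6000.

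**What to change.** - Protocol 6.10.5, and the eCRF if needed: assess relationship separately to SUBOXONE film and to RBP-6000, and say whether the latter includes RBP-6000 given in RB-US-13-0001.
- SAP 9.6.1.1 to 9.6.1.3: state which item feeds each table, with the SUBOXONE item for run-in related tables and the RBP-6000 item for TEAE related tables.
- Run-in tables: show missing causality on its own line.
- If only an RBP-6000 item was collected: do not label or present the run-in rows as SUBOXONE-related, and rely on the all-causality run-in tables already planned. This may be the realistic route, since SAP version 3.0 is for final reporting and an interim analysis has been run.

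The cost is one more causality entry per AE and a few SAP sentences, or the loss of a few supplementary rows. Two entries will not separate film from depot for systemic events just after Injection 1, because both deliver buprenorphine.
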